2.3 RISK/BENEFIT ASSESSMENT

2.3.1 KNOWN POTENTIAL RISKS

PRESSION completed a hazard analysis/risk assessment through design failure modes and effects analysis (DFMEA), classifying risk based on severity of harm and anticipated occurrence with the Wave PRO ECP system, in accordance with ISO 14971. As PRession has mitigated almost all risks of the Wave PRO device, only the residual clinical risks are discussed here.

The risk analysis identifies that the participant may experience minor abrasions, bruising and/or calf muscle soreness/tenderness from the pressure application during compression. Both abrasions and bruising can be minimized by using an interfacing layer, such as a tight-fitting knee-high sock or sleeve, between the participant’s skin and the compression sleeve of the Wave PRO. Calf muscle soreness/tenderness as a result of normal compressions during system operation is expected to resolve without medical intervention.

Known side effects for existing ECP systems on the market, including the predicate ACS NCP-2 device, include skin abrasion, bruising, muscle ache, blistering, and paresthesia (prickling sensation), all of which are also potential side effects of the Wave PRO ECP system. Side effects of ECP treatment are generally well tolerated and can be minimized with additional padding at the interface of the compression cuffs and the participant. Other side effects can be resolved with the application of topical creams.

Rare side effects of ECP may include skin breakdown and increase in adverse cardiac events.

Any discomfort during an ECP session will be recorded for each participant, along with any adverse events during testing.

2.3.2 KNOWN POTENTIAL BENEFITS

Predicate ECP devices are indicated for the treatment of chronic stable angina (CSA) by creating diastolic augmentation during cardiac diastole. As noted in the literature, ECP treatment “create[s] a pressure wave that significantly increases peak diastolic pressure, benefiting circulation to the heart muscle and other organs, while also reducing systolic pressure and systemic vascular resistance to the general benefit of the vascular system”³. “[ECP] has marked effects on the magnitude of diastolic retrograde and systolic antegrade blood flow in the descending aorta”¹. “[ECP] unequivocally and dramatically increases directly measured coronary flow velocity and pressure. This noninvasive counter pulsation technique generates a significant increase in diastolic pressure measured in the central aorta and the mid to distal coronary artery, representing diastolic augmentation”⁴. “Coronary blood flow velocity measured by both angiographic and intracoronary Doppler techniques is significantly increased during [ECP], whereas left ventricular afterload is reduced because of systolic unloading, thereby lowering left ventricular work”^{4,5}. ECP treatments have been shown to reduce angina class by at least one Canadian Cardiovascular Society (CCS) score in 86% of patients, decrease nitroglycerin usage by over 80%, and increase exercise tolerance by 25% in patients with refractory angina, with benefits sustained for up to five years⁶⁻⁸.

With compression of the calf muscles timed to the cardiac cycle, the Wave PRO ECP device imparts similar physiological and therapeutic benefits compared to commercially available ECP systems with anticipated greater patient comfort. Additional benefits include an ergonomically improved and lighter form factor and automation features controlling inflation and deflation timing, obviating the need for a dedicated technician to operate the system for all 35 treatment hours.

For the purposes of this study, participants are not expected to benefit from the two 10-min ECP sessions. However, data and knowledge acquired from this study are expected to positively impact future patients requiring ECP for anginal symptom relief.

2.3.3 ASSESSMENT OF POTENTIAL RISKS AND BENEFITS

The anticipated risks of the Wave PRO ECP system and this study protocol are minor and unlikely to cause serious harm to study participants. While study participants are not expected to gain any immediate health benefits, existing and future patients with CSA are expected to benefit from an ECP device that is more readily available and comfortable.

The Wave PRO ECP system does not meet any of the criteria defined by the FDA for a Significant Risk device, therefore the Sponsor considers this study to be Non-Significant Risk.

The Investigational Device Exemption (IDE) regulation (21 CFR 812) describes three types of device studies: significant risk (SR), nonsignificant risk (NSR), and exempt studies. An investigational device is considered NSR if it does not meet the definition for an SR device.

21 CFR 812.3(m) defines a Significant Risk device as an investigational device that:

1. Is intended as an implant and presents a potential for serious risk to the health, safety, or welfare of a subject;
2. Is purported or represented to be for use supporting or sustaining human life and presents a potential for serious risk to the health, safety, or welfare of a subject;
3. Is for a use of substantial importance in diagnosing, curing, mitigating, or treating disease, or otherwise preventing impairment of human health and presents a potential for serious risk to the health, safety, or welfare of a subject; or
4. Otherwise presents a potential for serious risk to the health, safety, or welfare of a subject.

Since the Wave PRO system does not meet any of the criteria defined by the FDA for an SR device, the Sponsors consider this study to be NSR.

Risk controls have been implemented to minimize harm to the user and the recipient of the ECP treatment. Per Pression's DFMEA and resulting Risk Management Report, residual risks associated with the Wave PRO and the controls implemented to reduce those risks are presented in the Risk Benefit Analysis below:

Risk	What are the Medical Benefits?	Risk-Benefit Analysis (Why do the medical benefits outweigh the residual risk?)	Is the Risk-Benefit Analysis Acceptable?
DFMEA 2.10.011 – 2.10.015 Electrical shock from the Control Unit resulting in death due to water intrusion, line cord abrasion or damage, poor dielectric protections, leakage current, and poor ground continuity	The benefits of the Control Unit are that it powers the device and provides timed air pressure pulses to the sleeves to provide ECP therapy. Without the Control Unit, the sleeves and connecting tubing would not provide the air needed for efficient ECP therapy for the patient.	Product safety testing was conducted to reduce electrical shock risks as far as possible, thereby reducing the rate of occurrence of these risks as far as possible. The expected clinical benefits outweigh the residual risk of electrical shock.	Yes
DFMEA 2.10.021 The Control Unit emits electromagnetic interference (EMI) that causes other nearby devices from operating properly, resulting in death	The benefits of the Control Unit are that it powers the device and provides timed air pressure pulses to the sleeves to provide ECP therapy. Without the Control Unit, the sleeves and connecting tubing would not provide the air needed for efficient ECP therapy for the	Product safety testing was conducted to reduce EMI risks as far as possible, thereby reducing the rate of occurrence of these risks as far as possible. The expected clinical benefits outweigh the residual risk	Yes

Risk	What are the Medical Benefits?	Risk-Benefit Analysis (Why do the medical benefits outweigh the residual risk?)	Is the Risk-Benefit Analysis Acceptable?
	patient.	of EMI.	

Per Pression's DFMEA and resulting Risk Management Report, the Benefit Risk Analysis is as follows:

What are the Overall Medical Benefits?	Risk-Benefit Analysis (Why do the overall medical benefits outweigh all risks?)	Is the Overall Risk-Benefit Analysis Acceptable?
The overall medical benefit of the Wave PRO device is to provide External Counter-Pulsation treatment to reduce angina symptoms in patients with chronic stable angina that is refractory to optimal anti-anginal medical therapy and without options for revascularization.	
Use of the Wave PRO ECP device carries risk from procedural error, inherent use hazards, and device failure. Pression LLC has taken measures to ensure the device is designed, manufactured, and tested appropriately to mitigate and control these risks through systematic risk analysis, in-process controls and final inspection, labeling, instructions for use, and usability testing. As a result, the residual risk is reduced as far as possible.
 
In conclusion, the benefits outweigh the risks in the use of the Wave PRO device.
	Yes

3 OBJECTIVES AND ENDPOINTS

OBJECTIVES	ENDPOINTS	JUSTIFICATION FOR ENDPOINTS
Primary		
	Performance/Effectiveness: DA Ratio of the Wave PRO system as compared to the predicate ECP device at the eighth minute of ECP compressions (out of 10 total compression minutes)	DA ratio was chosen as the primary endpoint of this study because it is a direct and objective measure of the hemodynamic effect of ECP. DA ratio is a unitless measure which is “calculated as the ratio of the peak diastolic amplitude divided by the peak systolic amplitude” ¹ . ECP causes diastolic amplitude to increase relative to systolic amplitude. DA ratio noninvasively characterizes the hemodynamic effect of ECP and is correlated to clinical effectiveness of the treatment, as described in the literature cited in this protocol. DA ratio can be measured by use of a second independent PPG sensor for the Wave PRO and by the onboard PPG sensor on the predicate ECP device. Due to these characteristics, DA ratio is an appropriate endpoint for assessing substantial equivalence of Wave to the predicate device.
Secondary		
	Safety: 
 ○ Occurrence of device-related Serious Adverse Events ○ Device-related Adverse Event rate 	Occurrence of device-related SAEs and AEs are appropriate endpoints for evaluation of safety because they are direct measures of the effect of the Wave PRO device on study participants. It is reasonable to consider only device-related AEs/SAEs and not all AEs/SAEs when evaluating the investigational device, as non-device-related AEs/SAEs will be irrelevant.

OBJECTIVES	ENDPOINTS	JUSTIFICATION FOR ENDPOINTS
	
Performance/Effectiveness:
 
 ○ The level of systolic unloading for the Wave PRO based on the systolic peaks during compressions compared to baseline of the PPG data, captured using the independent data acquisition system. ○ Number of participants that complete 10 mins of each of the ECP devices (Wave PRO and predicate ECP device) ○ Participant comfort level with the Wave PRO and predicate ECP device, assessed at the conclusion of each ECP session ○ Time to set up a participant (i.e., sleeved up and sensors attached) and ready to start treatment ○ Participant preference for one of the two ECP systems (assuming 35 hours for a full course of ECP) 	
 ○ Systolic unloading is a corollary to DA ratio discussed above and is a suitable secondary endpoint for the same reasons – it is a direct and objective measure of the hemodynamic effect of ECP. ○ Proportion of participants that completed the 10-minute treatment sessions is an appropriate endpoint because it is a surrogate measure of the tolerability of the Wave PRO device compared to the predicate ECP device. ○ Participant comfort levels is an appropriate endpoint because it is measured on a standard scale and reflects direct patient response to the two devices. ○ Tracking participant setup time enables Pression to quantify ease of use compared to the predicate ECP technology. It is appropriate as it quantifies the amount of time that can be reduced from patient visits and can help maximize treatments that clinical entities can provide in a day. ○ Participant preference for either one of the ECP systems helps validate the Wave PRO as a viable product with the potential of being more accessible for a population that may have limited mobility due to chest pain.

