- For the predicate ACS NCP-2 device: average DA ratio in the 8th minute of compressions will be calculated using an R script that processes the waveforms collected by the ACS software. The predicate device only allows for analysis of 8-second time strips at a time. No systolic unloading calculation for the predicate device.

During Signal Processing, the evaluator will be blinded to the paired participant testing (i.e., blinded to the participant ID). The blinded evaluator will not be able to match a participant's test on the Wave PRO with that of the predicate device. However, given the nature of the data collected, the evaluator will not be blinded to which ECP device the data pertains to. The

blinded evaluator will record the DA ratio in the CRF for each tested ECP device. For the Wave PRO, the blinded evaluator will also record the average systolic amplitudes.

Statistical analysis steps include (see Section 9)

- An ANOVA model for crossover design will be performed and the pairwise difference between two treatments DA ratios (Wave PRO – predicate ECP) in the treatment least square mean and its 95% CI will be constructed. Non-inferiority margin will be set at -0.15.
- Descriptive analysis will be conducted for all secondary endpoints.

During Statistical analysis, the statistician will be provided the DA ratio values (per ECP device) matched to each participant ID.

[figure not shown]

Figure 1: Study design schematic, including steps at the Clinical Site, Signal Processing, and Statistics. ¹Washout period between the ECP devices for each randomized participant will include walking around, ²Duration of setup will be recorded, ³Average DA ratio in the 8th minute of compressions (BIOPAC data, R script analysis), ⁴Average DA ratio in the 8th minute of compressions (ACS NCP-2 data, R script analysis), ⁵Average systolic amplitude of the last 10 waveforms of baseline and the systolic amplitude of the first 10 waveforms during compressions, ⁶Compared to non-inferiority margin (see stats description).

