DA ratio will be calculated by a qualified blinded evaluator (blinded to participant ID and ECP session pairing). A computer containing the ACS software (provided by Pression) will be used to review the ACS NCP-2 data and capture screenshots of the data, enabling the R script (provided by Pression) to process the data and calculate DA ratio, in accordance with the IFU. For the Wave PRO, raw data obtained from the dedicated BIOPAC data acquisition system will be evaluated using a separate custom R-script code (which Pression will provide). In effect, the same DA ratio calculation of the eighth minute of compressions for both systems will be conducted.

Internal testing has demonstrated that diastolic augmentation can be observed almost immediately at the start of an ECP session. The initial response of the participant to the ECP device can be assessed after the first 5 minutes of compression, so the 10 minute compression time is appropriate.

Per the ACS NCP-2 IFU regarding compression pressures on the first day (to be set by the operator at the clinical site), pressures will be set to 3PSI, from a maximum of 6PSI. Pressures are typically set to however much patients are able to tolerate, and more pressure does not always equate to higher augmentation in the predicate ECP device.

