6.1.2 WAVE PRO DEVICE TEST SESSION

This section pertains to the test session using the Wave PRO device with a participant that has been randomized.

- **Setup (approx. 10mins):** Time needed to get the participant ready for compressions will be recorded
 - Participant will be lying on the clinical bed with their back propped head-up at approximately 5° angle
 - Cotton stockinettes will be placed around the participant's legs between the knees and the ankles (if not already)
 - The clinical operator/technician will ensure that the Wave PRO is connected to an air supply source in the session room.
 - Clean air rated at 55 ± 1PSI.
 - Timer to record setup time will be started
 - The compression sleeves (with tubing attached) will be fitted around the participant's calves by a clinical operator/technician
 - The sleeves are differentiated by a left and a right sleeve
 - There are three different sleeve sizes (small, medium, large)
 - The sleeves are placed between the participant's ankles and knees
 - with the compression bands wrapped around the calf muscle
 - with the tubing ports on the medial side of the legs, pointing towards the feet
 - The compression sleeves should be snug against the participant's legs (tight but comfortable)

- The clinical operator should not be able to fit an index finger between the Compression Sleeve and the legs, but should not be so tight that the participant can feel their pulse through their leg
- **Rest (supine), blood pressure and heart rate (approx. 5 mins):** Participant should be completely set up and then asked to lie back and relax
 - Amount of time it took to set up will be recorded
 - The participant's systolic/diastolic pressures and heart rate will be recorded
- **Baseline PPG (2 mins):** With the Wave PRO system powered ON and on standby (not compressing), recording will be conducted to capture baseline PPG waveforms using the dedicated BIOPAC data acquisition system
 - Two PPG sensors will be placed on the participant's hand:
 - One for the Wave PRO
 - One for the dedicated Data Acquisition System
 - The sensors should be placed on the index (Wave PRO) and middle fingers (BIOPAC) on the right hand (if the Data Acquisition System signal is noisy, the sensor can be switched to another finger on the same hand)
 - The User Pause Button will be given to the participant to hold in the left hand
 - The User Pause Button allows the participant to temporarily stop the compressions at any time.

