- **Compressions (10mins):** The clinical operator/technician will begin compressions.
 - The ACS NCP-2 PPG sensor will be placed on the participant's right pointer finger
 - The clinical operator/technician will adjust the device pressure and the inflation and deflation timing based on the red and blue colored marker bars, respectively, on the monitor
 - The timing (red and blue colored marker bars) needs to be adjusted to generate a PPG waveform that has the appropriate shape (refer to IFU for inflation and deflation timing and resulting PPG waveform shapes)
 - As a starting point, the red colored region should start at the peak of T-wave (inflation) and the blue colored region should terminate just prior to the subsequent P-wave (deflation)
 - The 10 minutes of compressions start once the "Start Pump" button has been clicked (i.e., includes timing search)
 - PPG waveform data will be recorded on the ACS NCP-2 software (waveforms are only recorded when the pump is running)
 - Compression pressure will be increased in small increments until a maximum of 3 PSI is reached, per the ACS software readout
 - In accordance with pressure settings for the first day of ECP treatment per the predicate device IFU
 - 3 PSI will be reached as fast as possible along with the correct inflation/deflation timing

- **Stop compressions:** Compressions will be concluded by pressing the “Pump Start” button again after 10 mins have elapsed
 - Proper steps to exit out of the treatment screen will be followed to prevent loss of data
 - The participant’s profile will be revisited immediately to ensure that the test data was saved (Full Disclosure screen)
- **End-of-Session procedure:** The clinical operator/technician will perform the following:
 - The participant’s systolic/diastolic pressures and heart rate will be recorded
 - Participant questionnaire related to the ECP device will be conducted
 - ACS NCP-2 will be turned off (if applicable)
 - EKG leads and electrodes will be removed from the participant
 - Sensors will be removed from the participant’s finger
 - The three compression cuff sets will be removed from the participant
 - If this is the second test session, an observation period of approx. 10 minutes should be made available for each participant

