6.3 DATA ACQUISITION WAVE PRO

6.3.1 BIOPAC MP35 DATA ACQUISITION SYSTEM DESCRIPTION

The BIOPAC MP35 Data Acquisition system paired with the BSL 4.1 software will serve as the dedicated PPG waveform and data extraction system to acquire waveforms that will subsequently be used to calculate DA ratio and select secondary endpoints as a result of Wave PRO compressions. The MP35 is a four channel system with a 24-bit A/D sampling resolution. The MP35 is capable of recording 100,000 samples per second.

The BIOPAC SS4LA PPG Transducer, which connects to the 9-pin female DSUB connector on the MP35, will be attached to the participant’s finger using the built-in hook-and-loop strap to capture PPG signals. The SS4LA is a reflectance type PPG sensor that utilizes a matched infrared emitter and photo diode to detect changes in blood density due to blood pressure fluctuations. The emitter/detector wavelength is 860nm \pm 60nm, with a built-in low pass filter cutoff wavelength of 800nm.

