6.4 DATA ACQUISITION ACS NCP-2

6.4.1 ACS DATA ACQUISITION SYSTEM DESCRIPTION

The ACS NCP-2 software (NCPPLUS) records participant PPG and EKG waveforms throughout the duration of compressions. The ACS software will serve as the dedicated PPG waveform and data extraction system to acquire waveforms that will be used to calculate DA ratio as a result of ECP compressions on the ACS NCP-2.

The ACS PPG sensor is a transmission type PPG sensor that utilizes an infrared emitter and photo diode to detect changes in blood density due to blood pressure fluctuations.

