6.4.3 SIGNAL PROCESSING

After the ACS NCP-2 sessions are complete, data extraction will be conducted by the Statistician and data processing will be conducted by a blinded evaluator. Both the Statistician and blinded evaluator will be working under the requirements of an Analysis Charter.

- The Statistician will load the data from the secure data storage
- The Statistician will open each participant's ACS data file in the ACS NCP-2 Software (NCPPLUS)
- The Statistician will load the Full Disclosure page to access the test data
- The Statistician will use built-in Augmentation Cursor Screen capture all the waveforms within the 8th minute (i.e., minute 7 to minute 8) via screenshots
 - The onboard analysis tool uses 8-second strips. Each of these strips will need to be captured within the 8th minute
- The Statistician will upload the captured data to the secure data storage
- The evaluator will load the captured data from the secure data storage
- The evaluator must run the script and answer the prompts in the Console tab to have the script calculate the DA ratio
 - This script isolates PPG data from the screenshot files, analyzes the PPG data, prompts the user for key waveform features, and outputs DA ratio values, as well as the PPG waveform graphs

An Analysis Charter will be used to guide the evaluator through the process of extracting the DA ratio. The DA ratio values will be uploaded via CRF to the EDC.

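### Each device's DA ratio comes from its own sensor, finger, data route and script, so a measurement offset between the two chains cannot be told apart from a device difference

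*Combined protocol and SAP*

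**What the plan says.** Section 3 assigns the measurement by device: "by use of a second independent PPG sensor for the Wave PRO and by the onboard PPG sensor on the predicate ECP device". The later sections fill in the two chains.

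- **Sensor.** For Wave PRO (6.3.1): "The SS4LA is a reflectance type PPG sensor". For the predicate (6.4.1): "The ACS PPG sensor is a transmission type PPG sensor".
- **Finger.** Wave PRO session (6.1.2): "The sensors should be placed on the index (Wave PRO) and middle fingers (BIOPAC) on the right hand", with a switch to another finger of that hand allowed if the signal is noisy. Predicate session (6.2.2): "right pointer finger".
- **Data.** Wave PRO recordings are exported as .csv. Predicate recordings are opened in the ACS software and captured as PNG screenshots of 8-second strips (6.4.3, 10.1.7.3).
- **Script.** Section 4.2 says that the Wave PRO data "will be evaluated using a separate custom R-script code". The predicate script works from the screenshots.
- **Scoring.** The predicate script "prompts the user for key waveform features, and outputs DA ratio values" (6.4.3), and 6.3.3 describes similar prompts for Wave PRO. Section 4.1 states that "the evaluator will not be blinded to which ECP device the data pertains to".

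The plan also offers safeguards. The summary of changes says that both devices' data now go through the same processing steps, and 4.2 says that the calculation is in effect the same. The evaluator is blinded to participant ID and sequence (6.6), is independent of sponsor and investigators (8.2), and has no financial interest in the sponsor (10.1.10).

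**The concern.** The trial has one confirmatory claim: the mean DA ratio on Wave PRO is not more than 0.15 below that on the predicate. Every Wave PRO value comes from one measurement chain and every predicate value from the other. If the two chains would read the same pulse differently on average, that difference is part of the treatment estimate. It could produce a non-inferiority conclusion that Wave PRO has not earned, or deny one that it has. The problem cannot be repaired after the data are in, because no predicate session would have a recording on the common sensor.

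**Working it through.** **Step 1. Reproduce the plan's figure.** Inputs from 9.3.1: margin -0.15, true difference 0, SD of the paired difference 0.30, one-sided alpha 0.025, power at least 90%, 12% attrition.

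- Normal approximation: n = (0.30 × (1.960 + 1.282) / 0.15)² = 42.03, so 43.
- Noncentral t with n - 1 df: power is 0.893 at n = 43 and 0.900 at n = 44, so 44 pairs.
- Attrition: 44 / (1 - 0.12) = 50.

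The plan's 44 and 50 are correct.

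**Step 2. Can the analysis separate device from chain?** The model in 9.3.1 has sequence, participant within sequence, period, treatment and period-by-treatment terms. Chain takes the same two values as treatment in every row of data, so it is the treatment column. With b the mean offset (Wave PRO chain minus ACS chain):

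E(estimated difference) = true difference + b.

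Randomised order balances period effects, not b. In a simulated balanced crossover with true difference 0, a period effect and b = 0.05, the mean estimate was 0.050. The paired t-test and per-protocol analysis use the same values and carry the same b. The planned sensitivity analysis concerns missing data only. A larger sample narrows the interval around the shifted value.

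**Step 3. Which chain differences can give b ≠ 0?** Section 2.2 defines the DA ratio as diastolic peak amplitude over systolic peak amplitude in the same signal. If one sensor multiplies the whole signal by a constant k, the ratio is kD/kS = D/S, so pure gain cancels. A different baseline reference c gives (D + c)/(S + c), which does not cancel unless D = S. Filtering, pulse shape by sensor or finger, screenshot digitisation and prompted feature choice can also act unequally on D and S. Random error only widens the interval.

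**Step 4. What would an offset do?** SE = 0.30 / √44 = 0.0452. The documents give no value for b, so the values below are assumed.

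- False non-inferiority at a true difference of -0.15: noncentrality b / 0.0452.
- Power at a true difference of 0, with the offset against Wave PRO: noncentrality (0.15 - b) / 0.0452.

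| Size of b | Noncentrality at -0.15 | False non-inferiority (b favours Wave PRO) | Noncentrality at 0 | Power (b against Wave PRO) |
|---|---|---|---|---|
| 0 | 0 | 2.5% | 3.32 | 90% |
| 0.025 | 0.55 | 7.8% | 2.76 | 77% |
| 0.05 | 1.11 | 19% | 2.21 | 58% |
| 0.10 | 2.21 | 58% | 1.11 | 19% |

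Using 42 or 43 df does not change these rounded figures. An offset of about 0.015 already doubles the error rate to 5%. For scale, 0.05 is one third of the margin (0.05 / 0.15) and about 5% of the pilot predicate mean (0.05 / 0.93).

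**The case against.** The plan has taken real steps. The processing steps were aligned between devices with the stated aim of a fixed algorithm in place of subjective point placement. The evaluator is independent, has no financial interest, and cannot pair sessions or see the sequence. These safeguards limit evaluator bias and deserve credit. They do not touch an offset from sensor type, finger or screenshot digitisation, which arises before the evaluator sees anything.

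The plan also gives reasons for the two chains: Wave PRO cannot capture waveforms itself, the predicate can, and the predicate calculation follows its IFU. This explains BIOPAC in the Wave PRO session. It does not show that BIOPAC could not also run in the predicate session.

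Three stronger readings are tempting, and the documents do not support them.

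- *Any difference between the sensors passes in full into the result.* Pure gain cancels. Only a mean shift in the ratio itself carries through.
- *The evaluator's answers are biased by device.* The documents do not say what the prompts ask or how much discretion they leave. That detail sits in the Analysis Charter and a separate data analysis document, neither available here. Those documents may also hold signal-level checks that this review cannot see.
- *The result is biased, or biased towards Wave PRO.* No offset is reported in either direction. The percentages show sensitivity to an offset; they are not evidence that one exists.

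**Conclusion.** The point stands as a confounding problem. Device and measurement chain are fully aliased in the sole hypothesis test, no planned analysis can separate them, and the documents describe no agreement check between the chains and no validation of the screenshot extraction. That much follows directly from the text. The size of the consequence does not: it rests on assumed offsets of 0.025 to 0.10, an SD of 0.30, 44 pairs, and an offset that does not cancel in the ratio. On those assumptions the risk runs both ways, to the validity of a positive result and to the sponsor's chance of obtaining one. The sample size needs no correction. The point should be settled before enrolment, since it is cheap to fix then and cannot be fixed afterwards.

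**What to change.** - **6.2.2:** during predicate compressions, also record the BIOPAC SS4LA on the right middle finger, beside the ACS sensor on the index finger. No predicate baseline recording is needed for the DA ratio.
- **Primary endpoint:** compute the DA ratio for both devices from BIOPAC .csv files, using one locked script and the same prompt rules.
- **Masking:** give the files to the evaluator under treatment IDs without the device label. The file type would then no longer reveal the device, although waveform shape may still hint at it.
- **Supportive analysis:** keep the ACS-derived DA ratio, and report BIOPAC-ACS agreement within the predicate session.
- **Text to edit:** 4.1, 4.2, 6.2.2, 6.3.2 (the event keys are written for Wave PRO), 6.4 and the Analysis Charter.

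The cost is one extra finger sensor in the predicate session, possibly moving the BIOPAC unit between the two beds, and some risk of noisy recordings. The four-channel MP35, the transducer and the laptop are already supplied to the single site (6.3.1, 6.5.1), so no new equipment or staff are needed. The 44 pairs and 50 randomised stay as they are if the SD remains 0.30.

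If common recording is refused, the minimum is a prespecified tipping-point analysis. It would report the offset in Wave PRO's favour at which non-inferiority would be lost, which is the observed lower confidence limit plus 0.15. This discloses the dependence on an offset but does not remove it.
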